In hip and knee OA exercise is recommended as the first-line treatment (4). The effectiveness of exercise and the effectiveness of TSA in patients with glenohumeral OA is unknown, as no randomized trials have directly compared TSA to a non-surgical treatment (5). In order to provide a trustworthy and evidence-based foundation for clinical decisions it is important to conduct a randomized controlled trial where surgical treatment is compared to non-surgical treatment in patients with glenohumeral OA.

The primary aim of this trial is to examine if surgical treatment followed by standard care is superior to a 12-week exercise programme in patients with primary glenohumeral OA. The primary outcome is the Western Ontario Osteoarthritis of the Shoulder index score (WOOS), measured 12 months after initiating the treatment. The primary hypothesis is that surgical intervention is superior to the exercise intervention at 12 months (1).

The key secondary objectives are (1):

- To investigate the effectiveness of total anatomical shoulder arthroplasty followed by standard rehabilitation compared to a 12-week physiotherapist-supervised exercise programme, on (1) pain intensity, (2) activities of daily living, (3) use of analgesics and (4) shoulder-related quality of life in patients with glenohumeral OA.
- 2. To investigate the safety of total anatomical shoulder arthroplasty followed by standard rehabilitation compared to a 12-week physiotherapist-supervised exercise programme on occurrence of adverse events from baseline to 12 months after initiating the treatment, in patients with glenohumeral OA.

Exploratory objectives:

- 1. To investigate the external validity of the randomised controlled trial on total anatomical shoulder arthroplasty and physiotherapist-supervised exercise in patients glenohumeral OA by comparing patient characteristics and patient-reported WOOS scores from baseline to 12 months after initiating the treatment, in patients included in the randomised controlled trial versus those declining to participate but included in the follow-up cohort.
- 2. To investigate objectively measured physical upper extremity activity level from baseline to 12 months using tri-axial (Axivity, UK) accelerometers, in patients with glenohumeral OA eligible for total anatomical shoulder arthroplasty.
- 3. To assess the cost-utility of total anatomical shoulder arthroplasty followed by standard care compared to a 12-week physiotherapist-supervised progressive exercise programme on quality-adjusted life years (QALYs) gained from baseline to 12 months after initiating the treatment, in patients with glenohumeral OA.

SECTION 3: STUDY METHODS

Trial Design

The PROACT trial is a multicenter randomized controlled and investigator blinded trial, the reporting of the trial will follow the "*Consolidated Standards of Reporting Trials*" (CONSORT) statement (12). Patients are recruited from the orthopaedic departments at Aarhus University Hospital, Aalborg University Hospital, Viborg Regional Hospital and Silkeborg Regional Hospital in Denmark, at Tampere University Hospital, Central Finland Hospital in Finland and Oslo University Hospital in Norway.

The Statistical Analysis Plan (SAP) is reported in accordance with the "Guidelines for the Content of Statistical Analysis Plan in Clinical Trials" (13).

The PROACT trial is registered at www.clincaltrials.gov with the number NCT04845074. The Central Denmark Region Committee on Biomedical Research Ethics (Journal No 1-10-72-29-21) and the Danish Data Protection Agency (Journal No 1-16-02-199-21), The Regional Ethics Committee of the Expert Responsibility area of Tampere University Hospital (ref ETL R21089) and The Regional Committee for Medical and Health Research Ethics Region South-East Norway (Ref. 269784) have approved the trial.

Randomisation

The included patients will be randomised with a 1:1 allocation to TSA or exercise after their baseline assessment. The randomisation is stratified by recruitment site with randomly selected block sizes and done by a computer-generated list of random numbers using the randomization tool in Research Electronic Data Capture (REDCap), developed by an independent data manager (14). During the trial period administrators of the randomisation procedure are blinded to block sizes and randomisation sequence at all times.

Sample Size

The sample size is based on the expected between group difference in the WOOS end scores. The WOOS score 1 year after TSA surgery was 84.6 points in the Danish Shoulder Arthroplasty Registry in 2020 (7). The WOOS score after completing this exercise intervention in a feasibility study was 67 points (15). The assumed common SD was 27.1. The required power was set to 80%. Given a power of 0.80 to detect a difference between the two groups and using a two-sided significance level α =0.05, the estimated sample of each intervention group is 39 patients. Allowing for possible crossovers, loss-to follow-up and drop-outs the total number of patients in each group is 51 (1).

Framework

The overall objective of the trial is to determine whether surgical intervention results in a clinically and statistically significant greater improvement compared to exercise on WOOS, Disabilities of the Arm, Shoulder and Hand (DASH) (16), patient-reported pain intensity at rest, during activity, and nightly pain using the 100 mm VAS, the use of analgesics during the last week (paracetamol, NSAID, opioids) and adverse events. The primary hypothesis is that surgical intervention is superior to the exercise intervention at 12 months.

Blinded interpretation of the results

The blinded interpretation will be of the intention-to-treat analysis. The blinded analysis involves the primary outcome and key secondary outcomes. The principal investigator (JBL) will export data from REDCap and deliver the blinded dataset for analysis to the statistical analysist (AR). The senior statistician (EP) will supervise the analysis. The blinded results from the analysis of treatment A compared with treatment B will be presented to the project group followed by the development of the blinded interpretation. Interpretation version 1 assumes that group A had surgery, while interpretation 2 assumes that group A performed exercise. A draft of the blinded interpretation will be sent for approval by all co-authors. No other outcomes will be analyzed prior to an agreement of the blinded interpretation by all co-authors. All other analyses described in this document will be performed after the blinded interpretation is published (17).

Statistical interim analysis and stopping guidance

There has not been planned any formal statistical interim analysis for the PROACT trial. The final deadline for patient recruitment was a priori set to April 2024 but has since been moved to November 2024 due to delays in recruitment.

Timing of final analysis

The final analysis for the primary outcome, the end scores on WOOS at 12 months, will be performed after the last follow-up assessment at 12-months. The main publication of the trial will be prepared when these data are available.

In addition, papers on 2-, 5-, and 10-years follow-up will be performed, when these follow-up assessments are available.

Timing of outcome assessments

The trial consists of six time points; baseline, 12-weeks, 12-months, 2 years, 5 years and 10 years. An overview of the assessments and procedures has been presented in the protocol (Table 1).

SECTION 4: STATISTICAL PRINCIPLES

Confidence intervals and P values

For the primary outcome the statistical tests will be two-sided and a p-value <0.05 will be considered statistically significant. Confidence intervals will be 95% (95% CI) and two-sided. For the secondary outcomes the use of p values will be interpreted with care (18).

Adherence and protocol deviations

Adherence is defined as the ability to follow the allocated treatment. For the exercise group adherence is related to the number of attended supervised exercise sessions, good adherence has been predefined as participation in at least 70% of the supervised exercise sessions, during the first 12-weeks. Table 7 illustrates this.

There are predefined protocol deviations regarding adherence:

- 1. Patients randomized to exercise undergoing TSA in the follow-up period
- 2. Patients randomized to TSA not undergoing TSA in the follow-up period

Analysis populations

The primary analysis will be based on the Intention to Treat (ITT) principle. Patients allocated to a treatment group (TSA or exercise) should be followed up, assessed and analysed as members of that group, regardless of their adherence to the planned course of treatment.

Response to treatment will be described for both treatment groups, regardless of their adherence to the planned course of treatment.

A per protocol analysis will be conducted with patients in the surgical group undergoing surgery and for the exercise groups patients with a good adherence to the exercises are included. Poor adherence is defined as participating in less than 70% of the supervised exercise sessions. Another per protocol analysis will be of patients undergoing surgery regardless of randomization.

Lastly four as-treated analysis will be performed in which patients will be analyzed based on their adherence to the randomized treatment expecting four groups: (1) patients randomized to TSA and getting TSA, (2) patients randomized to exercise without undergoing TSA in the follow-up period, (3) patients randomized to exercise undergoing TSA in the follow-up period, (4) patients randomized to TSA not undergoing TSA in the follow-up period. One as treated analysis will be done on TSA patients versus good exercise adherence versus poor exercise adherence. And one as treated analysis on TSA patients randomized to TSA versus crossover TSA patients versus good exercise adherence versus poor exercise adherence.

SECTION 5: TRIAL POPULATION

Screening data

At all hospitals patients eligible for TSA will be screened for the inclusion and exclusion criteria. If they fulfil the criteria, they will be invited to participate. The number of patients who do not meet the criteria and the reason for ineligibility will be reported in a CONSORT flow chart (Figure 1).

Eligibility

Patients fulfilling the in- and exclusion criteria and are willing to participate are eligible for the PROACT trial. The inclusion criteria are:

Inclusion criteria:

- 1. Patients \geq 55 years
- Moderate to severe primary OA of the glenohumeral joint (Osteophyte larger than 3 mm, according to Samilson and Prieto (Samilson et al. 1983)
- 3. Eligible for surgery with standard TSA

Exclusion criteria:

- 1. Surgical need for bone graft or use of augmented glenoid component
- 2. Previous shoulder fracture (fracture of the proximal humerus or glenoid fracture)
- 3. Planned other upper extremity surgery within six months
- Rheumatoid arthritis or other types of arthritis not diagnosed as primary glenohumeral OA
- 5. Cancer diagnosis and actively receiving chemo-, immuno-, or radiotherapy
- 6. Neurological diseases affecting shoulder mobility (e.g., disability after previous stroke, multiple sclerosis, Parkinson's, Alzheimer's disease)
- 7. Other reasons for exclusion include mentally unable to participate or planned absence for more than 14 days in the first 3 months after baseline test
- 8. Unable to communicate in the respective languages of the participating countries.

Recruitment

The CONSORT flowchart will present the number of patients screened, excluded (with reasons), eligible for inclusion, randomized, receiving allocated treatment, withdrawals (with reasons), lost to follow-up (with reasons), included in the ITT analysis, included in the per protocol analysis.

Withdrawal/follow-up

Throughout the trial period the patients are allowed to withdraw from the study at any time. Patients who decide to withdraw will be encouraged to continue in the study as if they have received the intervention. Withdrawal will be classified into two options; (1) complete withdrawal from the study with no further follow-up and data-collection, (2) consent to follow-up assessments and data-collection. The number of withdrawals and the timing of withdrawal will be presented in the CONSORT flowchart (with reasons).

Baseline patient characteristics

Baseline characteristics will be presented as seen in Table 2. Categorical variables will be presented as numbers and percentages. Continuous variables will be presented as mean with

standard deviation (SD), if normally distributed and ad median with interquartile range (IQR) if not normally distributed. No tests of significance will be conducted for the baseline characteristics, imbalances of importance will be noted. Baseline and follow-up values for the primary and secondary outcomes will be presented as part of the analysis, as seen in Table 3.

SECTION 6: ANALYSIS

Outcome definitions

The Western Ontario Osteoarthritis of the Shoulder index score (WOOS)

The primary outcome will be presented as the between group difference on the 12-month follow-up score. WOOS is a valid and reliable patient-reported questionnaire assessing shoulder pain and function in a total raw score ranging from 0-1900, raw scores can be converted to a score from 0-100, where 0 indicates severe problems and 100 indicates no problems.

Key secondary outcomes

Disabilities of the Arm, Shoulder and Hand (DASH) (Lindenhovius et al. 2008); patientreported pain intensity at rest, during activity, and nightly pain using the 100 mm VAS; the use of analgesics during the last week (paracetamol, NSAID, opioids); serious adverse events and adverse events.

Analysis methods

Descriptive statistics will be presented as means with standard deviation (SD) for all normally distributed continuous variables. Continuous variables that do not follow a normal distribution will be presented as median with interquartile ranges. Normal distribution will be determined by visual inspection of QQ-plots and histograms. Categorical outcomes will be presented as numbers with percentages.

The primary comparison in WOOS between groups will be conducted using a linear mixed model. Intervention group and time (3 months, 12 months) will be included as fixed effects and patient as random. Baseline score, sex, age and study site will also be included as fixed covariates. Interaction between study group and time will be included in the model to estimate treatment effect at each time point. 95% confidence intervals are estimated for each time point.

Due to the repeated mixed model analysis no missing data imputation will be conducted. A sensitivity analysis will be done using an analysis of covariance (ANCOVA) including baseline score, sex, age and study site as covariates with the same ITT approach for time (3 months and 12 months) separately.

Analysis for patient-reported DASH, pain intensity at 3 and 12 months will be analysed similar to the primary comparison. For binary variables (ie. the use of analgesics and adverse events) we use proportions to describe the number of events. For each binary outcome an unadjusted risk difference in proportions with 95% confidence interval of outcomes between study groups. Table 3 illustrates the primary analysis.

Response to treatment for the WOOS change score from baseline to 12 months and 3 months follow-up will be computed for each patient in both treatment groups. Response to treatment will be presented dichotomized (i.e. responder and non-responder) as number and percentage. The patients will be classified as a responder if they reach a minimal important change of 13.3 points or more from baseline to 12 months follow-up (19).

Missing data

As stated above, imputations will not be applied in this study due to the repeated mixed model analysis. Each randomized patient will be included in the intention-to-treat analysis with the collected data. In an attempt to collect data from all randomized patients, patients deciding to withdraw from the study, are still encouraged to attend the follow-up test.

Harms

Adverse and serious adverse events will be presented as number and percentage for each event.

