	Baseline	Three months	One year	Baseline	Three months	One year	Adjusted
WOOS							
DASH							
Pain at rest							
Pain during							
activity							
Pain at night							
Use of							
analgesics*							
Adverse events*							
			Per-pr	otocol analy	ysis		
		TSA			Exercise		Improvement
							between the two
							groups
	Baseline	Three	One	Baseline	Three	One	Adjusted
		months	year		months	year	
WOOS							
DASH							
Pain at rest							
Pain during							
activity							
Pain at night							
Use of							
analgesics*							
Adverse events*							

Higher scores indicate desired (better) treatment outcome for WOOS. For the other outcomes lower scores indicate desired (better) treatment outcome.

*Analysed with risk difference, use of analgesics (yes/no), adverse events (yes/no).

	TS	Α		Ex	ercise		Cr	055-0V	er	No treatment		ıt	Improvements between the four groups	
	В	3M	1Y	В	3M	1Y	B	3M	1Y	В	3M	1Y	Adjusted	
WOOS														
DASH														
Pain at rest														
Pain during activity														
Pain at night														
Use of analgesics*														
Adverse events*														

Table 4: As treated analysis of the between group difference for the surgical group and exercise group in end-scores one year after intervention.

B=Baseline, 3M=Three months, 1Y=One year

Table 5: Usage of painkillers

		TSA group			Exercise gro	up
	Baseline	Three months	One year	Baseline	Three	One year
					months	
Use of painkillers, n (%) yes						
Type of painkillers, n (%)						
Paracetamol						
NSAID						
Morfin/opiods						
Other painkillers						
Usage of painkillers, n (%)						
Never						
Monthly						
Weekly						
Daily						

Table 6: Adverse and serious adverse events

	TSA group	Exercise group
Adverse events, n (%)		
Postoperative infections		
Instability		
Periprosthetic fracture		
Loosening		
Humeral component		
Glenoid component		
Both		
Injuries related to the exercise intervention		
Serious adverse events, n (%)		
Death		
Embolism		
Liver failure		
Renal failure		

*Serious adverse events resulting in the need for hospitalization or death in the first 4 weeks after surgery. Adverse events that occurred between baseline and 12 months follow-up but did not necessarily have a causal relationship between the treatments.

Table 7: Adherence to randomized treatment

	Exercise group
Training adherence	
Showed up for supervised sessions within the first three months of exercise, mean	
(SD)	

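### Could showing serious adverse events in the blinded A-versus-B step give away which arm had surgery?

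*SAP*

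**What the plan says.** Section 3, Blinded interpretation of the results, sets the scope twice: "The blinded interpretation will be of the intention-to-treat analysis", and "The blinded analysis involves the primary outcome and key secondary outcomes". Results are shown to the project group as treatment A against treatment B. Two readings are drafted, one for each possible identity of group A, and all co-authors approve them. The section adds "No other outcomes will be analyzed prior to an agreement of the blinded interpretation by all co-authors" and puts the SAP's remaining analyses after that step.

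Section 6, Key secondary outcomes, includes "serious adverse events and adverse events". Analysis methods treats adverse events as a binary outcome compared by an unadjusted risk difference, and states "Table 3 illustrates the primary analysis". Table 3 has one harms row, adverse events as yes/no, and none for serious events. Under Harms, the SAP says "Adverse and serious adverse events will be presented as number and percentage for each event"; Table 6 is the shell for that.

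**The concern.** Read literally, these parts do not quite meet. Serious adverse events are inside the blinded scope, the intention-to-treat shell has no place for them, and the only shell that names them is Table 6. That table lists postoperative infections, periprosthetic fracture, component loosening and exercise-related injuries. Its footnote places serious events in the first 4 weeks after surgery. A reader given those rows under A and B could often work out which arm was which.

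The rule against analysing other outcomes first does not settle this, because adverse and serious adverse events are in-scope outcomes. What would be at stake is the honesty of the word blinded: the two readings could be written by people who already know which one applies. The estimates themselves would not move.

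**Working it through.** **1. Which rows point to an arm?**

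| Outcome | Masked row in Table 3? | Rows in Table 6 | Do the row names identify a treatment? |
|---|---|---|---|
| Adverse events | Yes, pooled yes/no | Postoperative infections, instability, periprosthetic fracture, loosening, exercise injuries | Most do |
| Serious adverse events | No | Death, embolism, liver failure, renal failure | No; only the footnote refers to surgery |

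The outcome with revealing rows already has a masked display. The outcome without one has generic rows.

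**2. How much could a surgery-only count reveal?** The SAP gives no event or crossover rates, so these are assumptions: 51 operated TSA patients, c of the 51 exercise patients crossing over to TSA, and the same event rate p per operated patient. If the arm with more events is called surgery, and ties are guessed, then

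P(correct) = P(X_TSA > X_exercise) + 0.5 × P(tie), with X_TSA ~ Bin(51, p) and X_exercise ~ Bin(c, p).

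| p | c = 5 | c = 10 | c = 15 | Range of P(tie) |
|---|---|---|---|---|
| 0.5% | 0.601 | 0.589 | 0.577 | 0.73–0.76 |
| 1% | 0.678 | 0.656 | 0.635 | 0.56–0.58 |
| 2% | 0.785 | 0.750 | 0.716 | 0.35–0.36 |
| 5% | 0.928 | 0.887 | 0.843 | 0.10–0.15 |

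These figures describe the surgical rows of the adverse-event block. They carry over to serious events only if the Table 6 footnote is read so that operated patients alone can contribute.

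For the exercise-injury row, if only the 51 exercise patients can have an entry, P(at least one) = 1 − (1 − p)^51 = 0.226, 0.401, 0.643 and 0.927 at the same four rates.

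For the pooled yes/no row with 51 per arm, P(correct) is 0.500 at 10% v 10%, 0.636 at 10% v 8% and 0.831 at 10% v 5%.

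**3. How much does WOOS reveal anyway?** Inputs from Section 3, Sample Size: means 84.6 and 67, so a difference of 17.6; "The assumed common SD was 27.1"; 39 evaluable per group. The stated size reproduces: 2 × (1.960 + 0.842)² × (27.1/17.6)² = 37.2, so 38 by the normal approximation; the t-based calculation gives 38.2, so 39.

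The standard error of the difference is 27.1 × √(2/39) = 6.14. Calling the higher-WOOS arm surgery is right with probability Φ(d/6.14):

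| True difference d (TSA minus exercise) | P(correct) |
|---|---|
| 17.6 | 0.998 |
| 5 | 0.792 |
| 0 | 0.500 |
| −5 | 0.208 |

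Crossovers should dilute this too. If they gain the full TSA effect, d = 17.6 × (1 − c/51). For c = 5, d = 15.87 and P = 0.995; for c = 15, d = 12.42 and P = 0.979.

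**The case for a change.** The best case for acting is that blinding matters most when the result surprises. If WOOS does not differ, it gives no clue; if exercise is 5 points better, it misleads, with a guess right only 21% of the time. Those are the results most open to biased interpretation, and there a row for periprosthetic fracture or exercise injury could undo the masking. The SAP itself fixes the blinded step, the outcome list and the shells, so this is not a matter left to the protocol, and a sentence or two would settle it.

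Part of this stands. The display of serious events under A/B labels is unspecified, and the surgery-anchored footnote makes even a generic count lean towards the operated arm. It remains a gap in presentation, not a stated breach. The blinded step is tied to the intention-to-treat analysis, Table 3 is the shell with that title, and by-event description is set out separately under Harms. An analyst preparing an A-versus-B package would naturally use the pooled row and keep back rows that name a treatment.

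Taking serious events out of the blinded step altogether would also have a cost: a prespecified key secondary safety outcome would then be interpreted with the arms known. A pooled count of patients with any serious event, over a period common to both arms, keeps it in the step without naming a treatment, and analysts can produce that under the SAP as written.

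**Conclusion.** No change to the SAP is called for. The wording leaves open how serious adverse events appear in the blinded step, but it does not direct anyone to show Table 6 there, and the sensible way to fill the gap is plain. The rows that would reveal treatment concern ordinary adverse events, which are already masked in Table 3.

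At most, a surgery-only count would raise the chance of naming the arm from 50% to between 58% and 93%, at assumed rates of 0.5% to 5% with 5 to 15 crossovers. If the design difference holds, WOOS alone gives about 98% to 99.8%, so hiding harms rows would gain almost nothing. The gain lies in the less expected case of a small or reversed WOOS difference. Even then both readings must be drafted and agreed, and no estimate, interval or test is affected. The conclusion rests on the natural reading that the blinded package is the Table 3 intention-to-treat panel, and on analysts not circulating rows that name a treatment.

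### The exercise per-protocol set is defined by attendance alone, so a good attender who has TSA before month 12 stays in it and post-surgery data are reported as exercise

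*SAP*

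**What the plan says.** Under Adherence and protocol deviations (SAP Section 4), adherence is described in general as following the allocated treatment. For the exercise arm it is then made operational: "good adherence has been predefined as participation in at least 70% of the supervised exercise sessions, during the first 12-weeks". The same subsection names two predefined deviations. The first is "Patients randomized to exercise undergoing TSA in the follow-up period"; the second is its mirror image in the TSA arm.

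Under Analysis populations, the per-protocol analysis takes surgical patients who had surgery, and "for the exercise groups patients with a good adherence to the exercises are included". The complement is also given in terms of attendance: "Poor adherence is defined as participating in less than 70% of the supervised exercise sessions". A further analysis follows: "Another per protocol analysis will be of patients undergoing surgery regardless of randomization". No comparator is stated for it.

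The as-treated analyses come next. One of them has four groups, with TSA patients as randomised set against "crossover TSA patients versus good exercise adherence versus poor exercise adherence". The per-protocol half of Table 3 has only TSA and Exercise columns, each with baseline, three-month and one-year entries for WOOS, DASH, three pain scores, analgesic use and adverse events.

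**The concern.** The rule that decides membership closes at week 12, while the endpoint is at month 12. Whatever happens in between, including the comparator treatment itself, does not affect membership. The two arms are also treated differently: the TSA arm's deviation (no surgery) takes a patient out of the per-protocol set, but the exercise arm's deviation (surgery) does not.

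The result headed per protocol could thus contain exercise patients measured after a shoulder replacement. For binary outcomes Section 6 plans this: "For each binary outcome an unadjusted risk difference in proportions with 95% confidence interval of outcomes between study groups". Table 6 lists "Periprosthetic fracture" and component loosening, which require an implant, and its footnote counts adverse events from baseline to 12 months whether or not they are causally related to treatment. If a crossover had such an event, it would count in the exercise per-protocol risk.

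The situation is foreseeable. Every participant must be eligible for TSA, the sample size was raised partly for crossovers, and Table 1 records crossover at 3 and 12 months.

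**Working it through.** **Reading the definitions together**

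1. Good adherence (at least 70%) and poor adherence (less than 70%) are complements on attendance. Neither mentions TSA, so an exercise patient with 70% attendance and later TSA is a good adherer by definition.
2. No sentence says that a listed deviation leads to exclusion from the per-protocol set.
3. The last as-treated analysis sets crossovers and good adherers side by side as separate groups. There the term has to exclude crossovers, although its definition does not. The SAP therefore uses one term in two senses.
4. Table 7 counts 70% attendance and surgery after randomisation to exercise in separate rows, so one patient can appear in both.
5. If the second per-protocol analysis uses the good-adherence exercise group as comparator, a good adherer who crossed over belongs to both groups.

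**Inputs for size** (SAP Section 3, Sample Size): TSA mean 84.6, exercise mean 67, SD 27.1, two-sided alpha 0.05, power 80%, 39 per group, 51 after allowance.

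**The plan's own figure.** The planning contrast is 84.6 - 67 = 17.6. A two-sample t-test calculation gives 38.2, rounded up to 39 per group, which matches. The allowance is (51 - 39)/51 = 23.5% for crossovers, loss to follow-up and drop-outs combined; the crossover part is not given.

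**Shift in the contrast.** Let p be the share of good adherers who have TSA before month 12, and d their mean 12-month WOOS minus that of the other exercise patients (67). Then

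contrast = 17.6 - p × d.

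Both p and d are assumptions.

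| d | p = 10% | p = 20% | p = 30% |
|---|---|---|---|
| +17.6 (crossovers reach the TSA mean) | 15.8 | 14.1 | 12.3 |
| +8.8 (half that gain) | 16.7 | 15.8 | 15.0 |
| -8.8 (crossovers do worse) | 18.5 | 19.4 | 20.2 |

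The extremes are -0.3 × 17.6 = -5.3 and +0.3 × 8.8 = +2.6 points. The first row is an illustrative upper bound, because 84.6 is a score one year after surgery and crossovers would be less than a year out. If 39 is borrowed as the size of the exercise per-protocol set, the shares correspond to about 4, 8 and 12 patients; the SAP does not state that size.

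**Scale.** SE = 27.1 × √(2/39) = 6.14; t(76) = 1.99; unadjusted 95% CI half-width = 1.99 × 6.14 ≈ 12.2 points.

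**The case against.** The best defence is that Section 4 should be read as a whole. Adherence means following the allocated treatment, crossover is named first among the deviations regarding adherence, and a per-protocol set ordinarily leaves such patients out. The last as-treated analysis, where good adherers and crossovers are distinct, points the same way. This makes exclusion the probable intent. It does not supply the rule: the operational definition is attendance, it is given twice, and nothing links the deviation list to membership.

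Other points stand as limits on the finding:

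- The as-treated analysis in Table 4 separates crossovers from exercise patients without TSA, so a reader can see how crossovers fared, although those groups are not restricted to 70% attenders.
- The 30% scenario exceeds the whole 23.5% allowance. At 23.5% the extremes become -0.235 × 17.6 = -4.1 and +0.235 × 8.8 = +2.1.
- All the shifts lie within the CI half-width.
- Table 6 is not itself a per-protocol table, and adverse events in Table 3 are a single yes/no row, so the implant-event example only illustrates the mechanism.
- The double membership in the second per-protocol analysis depends on which comparator was meant.
- Excluding crossovers and discarding only their post-TSA data answer different questions. The choice belongs to the investigators.

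**Conclusion.** The concern holds and should be fixed. Followed literally, the text gives a per-protocol estimate contaminated by the other treatment; followed by intent, it needs a rule that is not on the page. The contamination falls mainly on the 12-month column, since the three-month scores of good attenders would mostly precede surgery. Its size cannot be derived from the SAP and its direction is unknown; the range calculated here rests entirely on assumed crossover shares and assumed scores after crossover. The damage is confined to the per-protocol results. In the ITT primary analysis it is right to keep crossovers in their randomised arm, and the blinded interpretation rests on ITT.

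**What to change.** Amend the per-protocol sentence so that the exercise set requires at least 70% attendance **and** no TSA before the 12-month assessment. Alternatively, keep crossovers' pre-TSA scores in the mixed model, set their post-TSA scores to missing, and count adverse events only up to TSA. State which of the two applies before the groups are unblinded. The explicit time limit matters because follow-up runs to 10 years.

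Use the same definition of good adherence in the as-treated analyses. Relabel the analysis of operated patients regardless of randomisation as as-treated, name its comparator, and make its groups mutually exclusive.

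The cost is one clause and one further sentence. No new data are needed, because crossover is already collected at 3 and 12 months. The downside is selection: either option removes post-TSA data from patients who probably did poorly on exercise. The SAP should therefore say that the per-protocol result is supportive only.
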